2.2. To investigate the relationships between food motives and the effect of an environmental label on ingredients and ready-to- eat dish selection in a virtual supermarket.	Mean of PEF scores for 100g of each ingredient selected and PEF score for 100g of the ready- to-eat dish.	
 
Environmental label (0= no / 1= yes)
 
The average ratings for items in the ethical subscale of the FCQ (Ethic_score)
 
Type of food (I / RTEd)
 
	Data from scenario 1 only (everyday scenario)	Mixed model analysis with random effect of participants. - PEF = labelling + Ethic_score + type_of_food + labelling* type_of_food + labelling* Ethic_score If label*type of food interaction is statistically significant: 2 ANCOVA models • For the 3 ingredients chosen (Task 1) - PEF = labelling + Ethic_score + labelling* Ethic_score • For the ready-ot-eat dish chosen (Task 2) - PEF = labelling + Ethic_score + labelling* Ethic_score

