### Variables for the secondary outcomes

- Labelling (presence (yes) vs. absence (no) of an environmental label)
- Scenario ("everyday scenario" vs. "environmentally friendly scenario")
- Type of food present in the virtual environment (Ingredients vs. Ready-to-eat dish)
- Ethical concern scores will be calculated for:
  - the items of the "Environmental Welfare" subscale from the Sustainable Food Choice Questionnaire (SUS-FCQ).
  - the items of the "Ethical" subscale from the French translation of the Food Choice Questionnaire (SUS-FCQ).

Each rating for individual items, such as "is produced in an environmentally friendly way", ranges from 1 to 4: 1 = Not at all important; 2 = A little important; 3 = Moderately important; 4 = Very important. Out of the two ethical concern scores described above, we will use the one with the highest Cronbach's alpha in the analyses. This score will be noted "*Ethic\_score*" and will be regarded as a continuous variable.

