### Secondary analyses

For the first secondary analysis (MODEL 2.1), mixed model analysis will be used to test the effect of *labelling* (categorical variable: yes or no), *type\_of\_food* (categorical variable: ingredients or ready-to-eat dish) and *labelling\*type\_of\_food* interaction on 4 dependent variables, with random effect of participants to account for correlation between repeated measures. We will only look at the data from the first scenario ("everyday scenario"). The 5 mixed model analysis that will be carried out are:

- FSA = labelling (categorical variable: yes or no), type\_of\_food (categorical variable: ingredients or ready-to-eat dish) and labelling\* type\_of\_food interaction
- Liking = labelling (categorical variable: yes or no), type\_of\_food (categorical variable: ingredients or ready-to-eat dish) and labelling \* type\_of\_food interaction
- Familiarity = labelling (categorical variable: yes or no), type\_of\_food (categorical variable: ingredients or ready-to-eat dish) and labelling\* type\_of\_food interaction
- Price per calories (€/kcal) = labelling (categorical variable: yes or no), type\_of\_food (categorical variable: ingredients or ready-to-eat dish) and labelling\* type\_of\_food interaction

If the *labelling\*type\_of\_food interaction* is not significant, it will be removed from the models.

ANOVA model will be used to test the effect of *labelling* (categorical variable: yes or no) on NOVA score for task 1 (for the 3 ingredients chosen). We will only look at the data from the first scenario ("everyday scenario").

- For the second secondary analysis (**MODEL 2.2**), we will only use "everyday scenario" data.
  - Mixed model analysis will be used to test the effect of *labelling* (categorical variable: yes or no), *type\_of\_food* (categorical variable: ingredients or ready-to-eat dish), *labelling\*type\_of\_food* interaction, *Ethic\_score* (continuous variable) and *labelling\* Ethic\_score* interaction on PEF scores, with random effect of participants to account for correlation between repeated measures. If the *labelling\*type\_of\_food* interaction is not significant, it will be removed from the model.

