  - If the interaction between the labelling condition and the type of food is statistically significant., two ANCOVA models will be carried out for the home-cooked dish (average of the 3 ingredients) and for the ready-to-eat dish separately. ANCOVA models will be used to test the effect of *labelling* (categorical variable: yes or no), *Ethic\_score* (continuous variable) and *labelling\*Ethic\_score* interaction on the mean PEF score.

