Data for participants in the "label condition" only	Mean PEF scores	
 
Attention paid by the participant to the label (0=they did not notice the presence of the label on the products chosen or thought that the label was present on less than half of the products chosen /1=the participant thought the label was present on all of the products chosen or on more than half of them)
 
Type of food (I / RTEd)
 
Scenario ("everyday scenario")
 
Use of the label by the participant (continuous variable ranging from 0 to 100)
 
Type of food (I / RTEd)
 
Scenario ("everyday scenario")
 
	Mixed model analysis

	
 
Time spent to carry out each shopping task (continuous variable)
 
Environmental label (0= no / 1= yes)
 
Type of food (I / RTEd)
 
	
	
 
Score obtained for the question regarding the knowledge about the environmental impact of food systems (continuous variable).
 
Environmental label (0= no / 1= yes)
 
Type of food (I / RTEd)
 
	
	(knowledge_score*labelling interaction will be interesting to analyse in order to test the moderating effect of knowledge on the environmental impact of food choices)	
Mean FSA scores	
 
The average ratings for items in the health subscale of the FCQ
 
Environmental label (0= no / 1= yes)
 
Type of food (I / RTEd)
 
	

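### Model 2.2 and its two per-task ANCOVAs test the label effect at an Ethic_score of 0, which is outside the 1 to 4 scale; the moderation test itself is unaffected

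*Combined protocol and SAP*

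**What the plan says.** The objective 2.2 row of the Overview of the statistical analysis gives the model as "PEF = labelling + Ethic_score + type_of_food + labelling* type_of_food + labelling* Ethic_score", using everyday-scenario data only and a random participant effect. The Secondary analyses section lists labelling, Ethic_score and their interaction among the effects this model tests. Its only removal rule concerns labelling*type_of_food, so labelling*Ethic_score always stays in.

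If labelling*type_of_food is significant, separate models follow for the home-cooked dish and the ready-to-eat dish: "ANCOVA models will be used to test the effect of *labelling* (categorical variable: yes or no"), together with Ethic_score and labelling*Ethic_score.

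Under Variables for the secondary outcomes, each item "ranges from 1 to 4: 1 = Not at all important". Ethic_score is the average of one of two subscales, whichever has the higher Cronbach's alpha, "and will be regarded as a continuous variable". Both subscales use the same 1 to 4 ratings. No section mentions centring, standardising, or a score at which the label effect will be estimated.

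The stated hypothesis for objective 2.2 is moderation: a stronger label effect in participants with greater ethical concern. The overall label effect belongs to objective 1.1 and Model 1.1, which does not contain Ethic_score.

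**The concern.** When a continuous moderator and its product with treatment are both in a model, the treatment coefficient is the treatment effect where the moderator equals zero. Sum-to-zero coding of the label, or a SAS Type 3 test, does not alter this for a continuous moderator. Here zero is an impossible score, so the labelling row is an extrapolation with an inflated standard error.

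A report could then show a clear label effect from Model 1.1 and none from Model 2.2, on the same participants and the same outcome. The per-task ANCOVAs deserve particular care. Model 1.1 specifies no follow-up by task when labelling*type_of_food is significant, and the per-task follow-up of Model 1.2 uses both scenarios. The ANCOVAs are thus the only prespecified per-task label tests on PEF that use the everyday scenario alone.

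**Working it through.** **The plan's own figure.** The Sample size section gives no figure for Model 2.2. It states 122 participants for 80% power at d = 0.50 and α = 0.05. A two-sided two-sample normal calculation gives N = 4 × (1.960 + 0.842)² / 0.50² = 125.6, that is 126; with N = 122 the power is 78.9%. This is a close but not exact match, and it does not bear on the present point.

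**What the labelling test estimates.** Write the part of the model that matters as b0 + b1·L + b2·E + b3·L·E, with L the label (0/1) and E the score. The label effect at score e is b1 + b3·e, so testing b1 tests the effect at e = 0. Equivalently:

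effect at 0 = effect at mean − mean × b3

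**Standard error.** With the score similarly distributed in both arms:

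SE at 0 / SE at mean = √(1 + (mean/SD)²)

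**Inputs.** From the plan: d = 0.50, α = 0.05 (taken as two-sided), 130 recruited at 1:1, so 65 per arm. Assumed, because the documents do not give them: Ethic_score mean/SD of 2.5/0.7, 3.0/0.6 or 3.2/0.5; between-task correlation 0.3; d = 0.5 in each task; outcome SD 1 per task; no moderation in the power figures.

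**Centred standard errors.**
- Mixed model, label effect averaged over the two tasks: the SD of a participant's mean is √((1 + 0.3)/2) = 0.806, so SE = 0.806 × √(2/65) = 0.141 and 0.5/0.141 = 3.54. Power is about 94%.
- Each ANCOVA: SE = √(2/65) = 0.175 and 0.5/0.175 = 2.85. Power is about 81%.

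**Uncentred power.** Divide those ratios by the SE inflation k, then power = Φ(ratio/k − 1.96) + Φ(−ratio/k − 1.96).

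| Mean/SD | k | Mixed model | Each ANCOVA |
|---|---|---|---|
| 2.5/0.7 | 3.7 | 16% | 12% |
| 3.0/0.6 | 5.1 | 11% | 9% |
| 3.2/0.5 | 6.5 | 9% | 7% |

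**Wider range.** Means from 2.0 to 3.5 and SDs from 0.5 to 0.8, with N = 122 and an effect of 0.50 SD of the analysed outcome, give k from 2.7 to 7.1. Power is 7-18% uncentred against about 79% centred. A simulation at mean 3.0, SD 0.7 (8,000 runs, scores kept within 1 to 4) rejected in 9% of runs uncentred and 77% centred. The interaction p-value was the same either way, to within 1e-12.

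**Sign.** With a label effect of −0.5 at the mean and moderation of −m SD per SD, the expected effect at 0 is −0.5 + m × mean/SD. It turns positive only if m exceeds 0.5 × SD/mean, which is 0.14, 0.10 and 0.08 in the three settings. The probability of a wrong-signed mixed-model estimate follows from the same standard errors:

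| m (SD per SD) | 2.5/0.7 | 3.0/0.6 | 3.2/0.5 |
|---|---|---|---|
| 0.05 | 27% | 36% | 42% |
| 0.10 | 39% | 50% | 56% |
| 0.20 | 66% | 76% | 80% |

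**The case against.** The strongest reply is that the affected test answers no stated hypothesis. Objective 2.2 asks about moderation, and that test is identical with or without centring. The overall label effect is assigned to Model 1.1. This stands, and it rules out a reading that a reader might otherwise infer: that the objective 2.2 test or a primary analysis is compromised. It does not remove the point, because the plan itself commits to testing labelling in these models, and the ANCOVAs have no everyday-only per-task counterpart on PEF.

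Second, the raw score is inferred from silence; the plan does not say that it will be left uncentred. That is true, but a plan that prints the formula and defines a 1 to 4 score is most plainly read that way.

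Third, one might infer that the label estimate must reverse sign if the moderation hypothesis is true. The arithmetic does not support this. Reversal is expected only above the thresholds shown, and the documents give no moderation size.

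Fourth, one might extend the point to the knowledge-score model in Table 6, where the plan says the "interaction will be interesting to analyse in order to test the moderating effect of knowledge". The documents give no range for that score, so zero may be attainable, and the analysis is exploratory. The extension is not supported.

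Finally, the power figures depend on an undocumented score distribution and between-task correlation. This also stands, which is why ranges are shown.

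**Conclusion.** The point holds in limited form. As written, the labelling tests in Model 2.2 and its two ANCOVAs refer to an Ethic_score of 0, a value the scale excludes. That follows from the algebra and needs no assumption beyond reading the score as uncentred.

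The size does rest on assumptions. Under those listed, the standard error is about 3.7 to 6.5 times too large for a label effect at a typical score, and the labelling tests become nearly uninformative. A non-significant or oppositely signed labelling row from these models would not be evidence against the Model 1.1 result.

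**What to change.** In the objective 2.2 row of the Overview and in the Model 2.2 text of Secondary analyses, for both the mixed model and the two ANCOVAs, state that the overall sample mean of Ethic_score (both arms pooled) is subtracted before labelling*Ethic_score is formed. State also that the label effect will be reported with confidence intervals at the mean and at one SD either side, keeping those values within 1 to 4. This also shows where on the scale the label lowers PEF, which a significant slope alone does not.

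The cost is one sentence in the plan, one data-step line and a few estimate statements. The fitted model, the interaction test, the data and the sample size stay as they are.

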## Description of variables

#### Dependent variables

#### Primary outcome

The primary outcome is the environmental impact of the food selected by the participants. The environmental impact of the food selection will be quantified using the PEF score in mPt for 100g of product throughout the life cycle of the products.

The environmental impact of the 3 ingredients (i) chosen during task 1 of each scenario is calculated by the mean of the PEF scores of each product  $(PEF_i)^7$ .

$$PEF_j = \frac{\sum_{i=1}^{i=3} PEF_i}{3}$$

<sup>6 We will calculate the average for the ethical subscale of the FCQ (Cottet et al. translation) and for the "environmental welfare" subscale of the SUS-FCQ. We will use the score with the highest Cronbach's coefficient.

<sup>7 eCO2 stands for CO2 equivalent

 $PEF_{j}$  is the environmental impact for 100g of the selection of the 3 ingredients (mPt/100g).  $PEF_{i}$  is the environmental footprint for 100 g of each ingredient i.

The environmental impact of the ready-prepared dish chosen (task 2 of each scenario) is assessed by the PEF score for 100g of this product.

#### Secondary outcomes

 The nutritional quality of the dishes chosen by participants is assessed by the FSA score (the British Food Standards Agency nutrient profiling system) (Rayner et al., 2009), as described for each product (Julia & Hercberg, 2017).

The nutritional quality of the home-cooked dish (j) chosen during task 1 of each scenario is calculated by the mean of the FSA scores of each of the 3 ingredients (i) composing the dish.

$$FSA \ score_j = \frac{\sum_{i=1}^{i=3} FSA_i}{3}$$

 $FSA_i$  scores are calculated for 100g of the ingredient i.

The nutritional quality of the ready-prepared dish chosen (task 2 of each scenario) is assessed by the FSA score for 100g of this product.

• The liking score of the home-cooked dish (j) is the average of the 3 ingredients (i).

$$Liking j = \frac{\sum_{i=1}^{3} liking i}{3}$$

For the ready-to-eat dish, we will directly use the liking score given by participants. The liking score ranges from 1 to 10, 10 being the highest degree of liking.

• The familiarity score of the home-cooked dish is the average of the familiarity score of the 3 ingredients selected.

Familiarity 
$$j = \frac{\sum_{i=1}^{3} familiarity i}{3}$$

The familiarity score of the ready-to-eat dish is directly used. Familiarity scores range from 1 to 5 (1=Never and 5=Very often).

 The NOVA score of the home-cooked dish is the average of the NOVA score of the 3 ingredients selected.

NOVA score 
$$j = \frac{\sum_{i=1}^{3} NOVA \ score \ i}{3}$$

The NOVA score of the ready-to-eat dish will not be analysed since, by definition, all of these foods will be categorised in category 4 (ultra-processed foods).

• The price per calorie of the home-cooked dish is the average of the price per calorie of the 3 ingredients selected. The price per calorie of the ready-to-eat dish is directly used.

Price 
$$\left(\frac{\epsilon}{kcal}\right) j = \frac{\sum_{i=1}^{3} price \ per \ calorie \ i}{3}$$

The price per calorie for one product will be calculated with the following equation:

$$Price \ per \ calorie_i \ (\frac{\epsilon}{kcal}) = \frac{Price_i(\epsilon) \times 100}{Weight_i(g) \times Energy \ density_i(\frac{kcal}{100g})}$$

Independent variables

### Variables for the primary outcomes

- Labelling (presence (yes) vs. absence (no) of an environmental label)
- Scenario ("everyday scenario" vs. "environmentally friendly scenario")
- Type of food present in the virtual environment (Ingredients vs. Ready-to-eat dish)

### Variables for the secondary outcomes

- Labelling (presence (yes) vs. absence (no) of an environmental label)
- Scenario ("everyday scenario" vs. "environmentally friendly scenario")
- Type of food present in the virtual environment (Ingredients vs. Ready-to-eat dish)
- Ethical concern scores will be calculated for:
  - the items of the "Environmental Welfare" subscale from the Sustainable Food Choice Questionnaire (SUS-FCQ).
  - the items of the "Ethical" subscale from the French translation of the Food Choice Questionnaire (SUS-FCQ).

Each rating for individual items, such as "is produced in an environmentally friendly way", ranges from 1 to 4: 1 = Not at all important; 2 = A little important; 3 = Moderately important; 4 = Very important. Out of the two ethical concern scores described above, we will use the one with the highest Cronbach's alpha in the analyses. This score will be noted "*Ethic\_score*" and will be regarded as a continuous variable.

### Other variables

#### Socio-demographic characteristics

- Gender: 0=male, 1=female
- Age: continuous variable
- The level of education: This variable will be coded as the highest educational qualification from 1 to 4: 1= "< High school + 2-years diploma", 2= "high school + 2-years diploma", 3= "High school + 3 or + 4-year diploma" and 4 = "≥ High school + 5-year diploma".

- Employment status: The employment status of the participant will be coded from 1 to 6: 1 = "full or part-time", 2="student", 3="retired", 4="looking for a job", 5="looking after home" and 6="other".
- *The number of people living in the household:* this will be regarded as a continuous variable.
- Dieting status: 0 = no, 1 = yes.
- BMI: BMI will be calculated as weight (kg) / height (m^2). BMI data will be trimmed for implausible values excluding weight for less than 30 kg and more than 250 kg, height for less

than 145 cm and more than 3m, BMI < 14, or BMI > 48 (Hardy et al., 2016; Miller, 2003). We will use the BMI as a continuous variable or use the categories defined by the WHO.

### Missing data

We do not anticipate missing data for our analysis. It will be impossible for the participant to finish the shopping scenarios without having selected the 8 products. We have calculated the FSA-NPS scores and the PEF score for all of the products presented in our virtual supermarket.

We do not anticipate missing data for the dependent variables because the questionnaires will not allow missing answers. Data from participants who start but do not finish the study will not be included. Any *a posteriori* withdrawal will be reported and reasons for withdrawal will be documented (e.g., incorrect answers, technical problems).

### Primary analyses

**MODEL 1.1:** Mixed model analysis will be used to test the effect of *labelling* (categorical variable: yes or no), *type\_of\_food* (categorical variable: ingredients or ready-to-eat dish) and *labelling\* type\_of\_food interaction* on PEF scores in the "everyday scenario", with random effect of participants to account for correlation between repeated measures. If the *labelling\*type\_of\_food interaction* is not significant, it will be removed from the model.

#### MODEL 1.2:

- Mixed model analysis will be used to test the effect of *labelling* (categorical variable: yes or no), *type\_of\_food* (categorical variable: ingredients or ready-to-eat dish), *scenario* (categorical variable: "everyday scenario" or "environmentally friendly scenario"),*labelling\*scenario*, *labelling\*type\_of\_food* and *scenario\*type\_of\_food* interactions on PEF scores, with random effect of participants to account for correlation between repeated measures. Non-significant interactions will be removed from the model.
- If the *labelling\*type\_of\_food* or the *scenario\*type\_of\_food* interaction is **statistically** significant, two mixed model analysis will be carried out for the home-cooked dish (average of the 3 ingredients) and for the ready-to-eat dish separately. These models will test the effect of *labelling* (categorical variable: yes or no), *scenario* (categorical variable: "everyday scenario" or "environmentally friendly scenario") and *labelling\*scenario* interaction on PEF scores, with random effect of participants to account for correlation between repeated measures.

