1.1 To study the effect of an environmental label on the environmental impact of ingredients and ready- to-eat dish choice in a virtual supermarket.	Mean of PEF  score for 100g of each ingredient selected and PEF score for 100g of the ready-to-eat dish in the "everyday scenario".	
 
An environmental label will lower the environmental impact of the food choices made by the participants compared to no label.
 
The effect of the environmental label will be greater when choosing a ready-to-eat dish compared to when choosing ingredients.
 
				
1.2 To investigate whether the environmental label is informative and likely to help individuals to choose environmentally friendly food options when they	Mean PEF score for 100g of each ingredient selected and PEF score for 100g of the ready-to-eat dish in the "everyday scenario" and the "environmentally-friendly scenario".	
 
The reduction of the environmental impact of the foods chosen in the "environmentally-friendly scenario" compared to the "everyday scenario" will be greater for participants in the
 
				

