## EXPERIMENTAL DESIGN

[figure not shown]
This study will be a randomised controlled trial with two experimental arms:

[figure not shown]
- 1/ No label (no label condition)
- 2/ Environmental label (label condition)

A 2-block randomisation sequence (male and female) of 1:1 will be generated to allocate each participant to one of the experimental arm before recruitment using the Random Allocation software (Saghaei, 2004).

Each participant will be asked to perform two hypothetical shopping tasks in a virtual shopping environment, first in an "everyday scenario": 1/ choice of 3 ingredients for an everyday home-cooked dish among 66 products, 2/ choice of a ready-to-eat dish for an everyday meal among 30 products. The order of presentation of the two tasks will be counterbalanced. Then, the participants will be asked to perform the same two tasks while choosing foods for a dish that is "good for the planet" ("environmentally-friendly scenario"). For a given participant, the order of presentation of the two tasks will remain the same as in the everyday scenario.

The experimental design is described **Figure 1**.

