## STATISTICAL ANALYSES

All statistical analyses will be performed using SAS version 9.4. The level of significance will be set at p < 0.05 for all pre-registered analyses.

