### Overview of the statistical analysis

impact of ingredients and ready-to- eat dish choice in a virtual supermarket.		- Type of food (I  / RTEd  )		If label*type_of_food interaction is not significant, it will be removed from the model.
1.2. To investigate whether the environmental label is informative and likely to help individuals to choose environmental- friendly food options when they are encouraged to make environmental- friendly food choices.	Mean of PEF score for 100g of each ingredient selected and PEF score for 100g of the ready- to-eat dish.	- Environmental label (0= no / 1= yes) - Scenario ("everyday scenario"/ "environmental- friendly scenario") - Type of food (I / RTEd)	Data from the two labelling conditions and the two scenarios	Mixed model analysis with random effect of participants. Mixed model analysis with random effect of participants. PEF = label (0/1) + type_of_food ( I/RTEd ) + scenario (everyday/environmental) + label*type_of_food + label*scenario + scenario*type_of_food Non-significant interactions will be removed from the model. If the labelling*type_of_food or the scenario*type_of_food interaction is statistically significant: • For the 3 ingredients chosen (Task 1) PEF = labelling + scenario + labelling * scenario • For the ready-ot-eat dish chosen (Task 2) PEF = labelling + scenario + labelling * scenario

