### Sample size

We powered primary analyses in order to detect a d=0.50 effect size of labelling on PEF scores based the results of a previous randomised control trial that tested the effect of an environmental label on food choices (Camilleri, 2019). A sample size of 122 participants will be required for 80% power at  $\alpha$  = 0.05 (SAS 9.4). We will recruit a sample of 130 participants to account for potential data loss due to technical problems.

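### In pooled Model 1.2 a participant random effect alone does not assure 5% type I error for the primary label × scenario test; an arm comparison of each participant's change does, at almost no cost

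*Combined protocol and SAP*

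**What the plan says.** In the objectives table, row 1.2 is a primary objective. Its hypothesis begins "The reduction of the environmental impact of the foods chosen in the" environmentally-friendly scenario, and states that this reduction will be larger with the label than without it. That is a difference between arms in a within-person change, so label × scenario is its test.

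Under Experimental design, after the everyday scenario "the participants will be asked to perform the same two tasks while choosing foods for a dish that is" good for the planet. Each participant therefore has four PEF values. The overview table pools all four in one model with the interactions "label*type_of_food + label*scenario + scenario*type_of_food" and no three-way term. Primary analyses, Model 1.2, describes tests of these "interactions on PEF scores, with random effect of participants to account for correlation between repeated measures".

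If label × type of food or scenario × type of food is significant in the pooled model, separate models are fitted for the home-cooked dish and the ready-to-eat dish. The sensitivity analyses concern Model 1.1 only. On significance, the plan says: "The level of significance will be set at p < 0.05 for all pre-registered analyses".

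**The concern.** The natural reading of a participant random effect is a random intercept. It assumes one common correlation among the four values: same scenario with different food, same food with different scenario, and neither shared. The model then estimates one residual variance and uses it for every within-person test, although label × scenario depends only on how variable people are in their response to the scenario.

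Both kinds of departure are plausible. People may differ widely in how they respond to an instruction to choose for the planet, which makes the test liberal. They may also have stable preferences within each task, since the same products are offered twice, which makes it conservative. In the first case a p-value just under 0.05 overstates the evidence for a primary hypothesis; in the second, power is lost. Nothing else in the plan would reveal either.

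**Working it through.** **Inputs.** From the plan: four PEF values per participant (overview table, row 1.2); 130 recruited (Sample size) with 1:1 allocation (Experimental design), so 65 per arm; α = 0.05, taken as two-sided because the plan does not say. Assumed, because the documents give none: all correlations and SDs.

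**The plan's own figure.** There is none for this test. The only one is 122 participants to "detect a d=0.50 effect size of labelling on PEF scores", which concerns the label effect. For reference, 2 × (1.96 + 0.842)² / 0.5² = 62.8, so 63 per arm or 126 in total; the t test needs 128. Power at 122 is 78.2% by the t test. This does not enter what follows.

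**Step 1: contrast variances.** Take equal variances σ² and correlations a (same scenario, other food), b (same food, other scenario) and c (neither shared).
- scenario: σ²(1 + a − b − c)
- food: σ²(1 − a + b − c)
- scenario × food: σ²(1 − a − b + c)

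**Step 2: what the model uses.** The random-intercept residual estimates their average, σ²[1 − (a + b + c)/3]. Label × scenario needs the first contrast only. The ratio of true to assumed variance is

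λ = (1 + a − b − c) / [1 − (a + b + c)/3].

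The test is liberal when a > (b + c)/2, conservative when a < (b + c)/2, and exact at equality, of which compound symmetry is one case. Large-sample size is 2[1 − Φ(1.96/√λ)].

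**Step 3: numbers** (simulation: 60,000 trials per setting, 65 per arm).

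| a/b/c | λ | Size by formula | Size simulated |
|---|---|---|---|
| 0.2/0.2/0.2 | 0.80/0.80 = 1.00 | 5.0% | 5.1% |
| 0.2/0.2/0.1 | 0.90/0.833 = 1.08 | 5.9% | 5.9% |
| 0.3/0.2/0.1 | 1.00/0.80 = 1.25 | 8.0% | 7.9% |
| 0.3/0.1/0.05 | 1.15/0.85 = 1.35 | 9.2% | 9.1% |
| 0.3/0.5/0.1 | 0.70/0.70 = 1.00 | 5.0% | 5.1% |
| 0.2/0.4/0.1 | 0.70/0.767 = 0.91 | 4.0% | 4.0% |
| 0.1/0.4/0.1 | 0.60/0.80 = 0.75 | 2.4% | 2.5% |

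The participant-level change test stayed at 4.8–5.2% throughout. Unequal SDs with equal correlations matter little (4.7–5.8%).

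**Step 4: a second parameterisation.** Let s and t be the participant × scenario and participant × food variances relative to the residual variance. Then λ = (1 + 2s)/[1 + 2(s + t)/3].
- s = 0.25, t = 0: 1.5/1.167 = 1.29, size 8.4%
- s = 0.5, t = 0: 2/1.333 = 1.5, size 11.0%
- s = 0, t = 0.5: 1/1.333 = 0.75, size 2.4%
- t = 2s: exactly 5%

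A separate simulation (10,000 trials per setting, 61 and 65 per arm, some with skewed data) agreed, with the change test at 4.6–5.4%.

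**Step 5: the split.** The per-task models have two values per person. There the random-intercept test is the change-score t test, so the problem does not arise. They run only if a food interaction is significant, and those trigger tests use the same pooled residual. At a nominal 5%, label × food rejects in 11.2% of null trials at 0.1/0.4/0.1, and scenario × food in 2.4% at 0.3/0.2/0.1. With no food interaction, the pooled test stands in 93% of trials at 0.3/0.2/0.1.

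**Step 6: power for a 0.4-SD difference between arms in mean change.**

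| a/b/c | Pooled test | Change test |
|---|---|---|
| 0.2/0.2/0.2 | 72.3% | 71.8% |
| 0.3/0.2/0.1 | 70.1% | 62.0% |
| 0.1/0.4/0.1 | 75.0% | 83.2% |

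In the middle row the pooled test's higher figure comes from its 7.9% type I error.

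**The case against.** **The split will often replace the pooled test.** The plan itself expects a larger label effect for ready-to-eat dishes, stated for the everyday scenario, and label × food is one of the triggers. At 0.3/0.2/0.1, with a label × food effect of 0.2, 0.3, 0.4 or 0.5 SD, the pooled test stands in 73%, 50%, 27% or 11% of trials. With scenario × food also at 0.3 SD alongside label × food at 0.3 SD, it stands in 27%, and pooled false positives make up 2.2% of all trials. This limits the reach of the problem and stands as far as it goes. Where the pooled test is the one reported, however, its error remains 7.5–8.1%, and the plan cannot know in advance which branch it will take.

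**Inflation is possible, not shown.** This is correct. Ordinary values such as 0.2/0.3/0.1 give λ = 0.8/0.8 = 1 and nominal size. The point is that the plan leaves the size to chance.

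**The remedy has limits.** The change test alone leaves the trigger tests as they are. With the added random terms, the scenario component is estimated at zero in about half of trials at 0.2/0.2/0.2 and at 0.1/0.4/0.1, and there the fit is not identical to the change test. Both remarks are fair and bear on how the fix is worded. The lower power at 0.3/0.2/0.1 is not a real cost, because it is the removal of excess error.

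**Conclusion.** The concern holds. The size of a primary test depends on a covariance assumption that the plan neither states nor supports. Over the assumed correlations it runs from 2.5% to 9.1% against a nominal 5%; the direction cannot be settled from the documents. The result rests on reading the participant effect as a random intercept, two-sided testing, 65 per arm and the assumed correlations. It applies to pooled Model 1.2 and its two trigger tests. Model 1.1 and the per-task models, with two values per person, are unaffected. This is a cheap improvement to make before analysis, not evidence that the trial's result would be wrong.

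**What to change.** Pre-specify the test of hypothesis 1.2 as a two-sided two-sample comparison between arms of each participant's mean PEF change (environmentally-friendly minus everyday, the two tasks weighted equally). State also whether this test is reported when the split is triggered, with the per-task models as follow-up, or whether the split replaces it.

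Alternatively, keep Model 1.2 and add participant × scenario and participant × type-of-food random effects with Kenward-Roger degrees of freedom. In this balanced design that gives the same label × scenario test when both components are estimated above zero, and it also corrects the two trigger tests.

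If an unstructured covariance is preferred, add label × scenario × type of food and estimate the equally weighted label × scenario contrast. Without that term the tasks are reweighted: at 0.3/0.2/0.1 with task SDs of 1 (ingredients) and 0.5 (ready-to-eat), the weights become 0.125 and 0.875.

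The cost is one sentence and a t test, or two extra random terms in SAS. Complete data are expected, since "It will be impossible for the participant to finish the shopping scenarios without having selected the 8 products". If the random-intercept structure is true, power falls from 72.3% to 71.8% for a 0.4-SD effect. The change does not address the removal of non-significant interactions or the number of primary tests, which are separate matters.
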